6 SAFETY DATA

6.1 General Considerations

6.1.1 Analysis population

The safety population will be used for safety analyses of AEs, SAEs, clinical laboratory data, [REDACTED] data, ECG data and vital sign data. The safety MRI population will be used for the analysis of safety MRI data.

6.1.2 Visit windows

Visit windows will be mutually exclusive, contain no gaps, and end at the midpoint between scheduled post-baseline visits, with the midpoint itself assigned to the subsequent visit window. If two or more evaluations occur in the same visit window, the evaluation closest to the target visit day will be selected for inclusion in the analysis. If multiple evaluations on different days are equally close to the target visit day, then the latest evaluation will be selected for inclusion in the analysis. If multiple evaluations occur on the same day, the earliest value will be chosen for analysis if time of collection is available; a scheduled value will be chosen before an unscheduled or early discontinuation record.

6.1.3 Incidence, incidence proportion, and incidence rate

- Incidence and incidence proportion will be provided in incidence proportion tables. Incidence is defined as the number of subjects who experienced an event. Incidence proportion is defined as the number of subjects who experienced an event divided by total number of subjects in the analysis population, i.e., percentage. Each subject will be counted only once within each category.
- Incidence and incidence rate will be provided in incidence rate tables. Follow-up adjusted incidence rate will be used and is defined as the number of subjects with an event divided by the total follow-up time among the subjects in the analysis population (e.g., incidence rate per 100 subject-years). The total follow-up time (subject-years) is the sum of all subjects' follow-up time, where a subject's follow-up time is calculated as the number of days (inclusive) from first dose of study drug until the last day on study, divided by 365.25. For analyses of events after treatment discontinuation, time after treatment discontinuation will be used to compute total follow-up time. Each subject will be counted only once within each category.

6.2 Clinical Adverse Events

6.2.1 Treatment-emergent AEs (TEAEs)

All AEs will be analyzed based on the principle of treatment emergence. A treatment-emergent AE was defined as an AE that started or worsened after the start of first dose of study drug.

To define treatment emergence for AEs with missing start or stop date or time the following additional criteria will be used:

- if both the start and stop dates for a particular AE are missing, then that AE is considered treatment emergent;
- if the start date for a particular AE is missing and the stop date/time falls after the first dose date/time, then that AE is considered treatment emergent;
- if the start date for a particular AE was the same as the first dose date, and the start time was missing, then that event is considered treatment emergent.

For AEs with a partial start date, the year/month of the event date will be compared to that of the first dosing date to determine whether the event is treatment emergent.

In addition, SAEs that occurred since a subject was screened in the study and prior to the first infusion of study drug, which by definition are not treatment-emergent, will be included in relevant listings but will not be summarized.

Only TEAEs will be included in the AE tables, unless otherwise specified. All SAEs (including pre-dosing SAEs) will be included in the listing of SAEs, with an indicator for pre-dosing SAEs. Only TEAEs will be included in other AE listings, if not otherwise specified.

6.2.2 Summary and incidence analysis

Overall summary of AE table will summarize the number of subjects with any AE, with any AE by maximum severity (as assessed by the investigator), the number of subjects with any related AE (related to study drug as assessed by investigator), the number of subjects with SAE, the number of subjects with related SAE, the number of subjects with AE leading to study drug discontinuation, and the number of fatal AEs.

The sorting order for AE incidence tables, unless otherwise specified, will be by decreasing frequency order of “BIIB092” column. A subject is counted only once within each category in each table. For example, for the table of AEs by SOC and PTs sorted by decreasing frequency presented by treatment group, SOC will be presented in decreasing frequency order of BIIB092 column, and within each SOC, PTs will be presented in decreasing frequency order of BIIB092 column. A subject is counted only once within each SOC and PT.

The following AE incidence tables will be provided:

1. AEs by SOC and PT
2. AEs by SOC and PT sorted by alphabetical order
3. AEs by SOC, high level group term and PT

4. AEs by SOC
5. AEs by PT
6. AEs with at least 2% higher incidence for BIIB092 compared to placebo by SOC and PT
7. AEs with at least 2% higher incidence for BIIB092 compared to placebo by 12-week intervals by SOC and PT
8. AEs with an incidence of 2% or more in any treatment group by 12-week intervals by PT
9. AEs with an incidence of 2% or more in any treatment group by PT

10. AEs with an incidence of 5% or more in any treatment group by PT
11. Severe or very severe AEs by SOC and PT
12. Severe or very severe AEs by PT
13. AEs by maximum severity by SOC and PT. (SOC will be presented alphabetically. PTs will be presented in decreasing frequency order. Maximum severity will be presented within each PT in the order of mild, moderate, severe, very severe, unknown and total. A subject will be counted only once at the maximum severity within each SOC and PT.)
14. AEs by maximum severity by PT. (PTs will be presented in decreasing frequency order. Maximum severity will be presented within each PT in the order of mild, moderate, severe, very severe, unknown and total. A subject will be counted only once at the maximum severity within each PT.)
15. Related AEs by SOC and PT
16. SAEs by SOC and PT
17. SAEs by PT
18. Related SAEs by SOC and PT
19. AEs that led to discontinuation of study treatment by SOC and PT
20. SAEs with fatal outcome by SOC and PT
21. AEs by 12-week intervals by SOC and PT
22. SAEs by 12-week intervals by SOC and PT

The following listings will be provided.

1. Listing of AEs
2. Listing of SAEs (including pre-dosing SAEs)
3. Listing of AEs that led to discontinuation of study treatment
4. Listing of SAEs with fatal outcome

6.2.3 Adverse event of special interest

Immunogenicity is an AESI in the BIIB092 clinical development program. Adverse events representing potential immune/hypersensitivity reactions will be identified using customized MedDRA search criteria: Anaphylactic reaction, Angioedema, and Severe cutaneous adverse reactions via SMQ (narrow and broad) search; Eosinophilia, and Miscellaneous terms. Further details are given in Appendix 11.3.

An incidence proportion table for potential immune/hypersensitivity reactions organized by SMQ/Miscellaneous categories and by PT (for both AEs and SAEs), and similarly for potential immune/hypersensitivity reactions for subjects with and without treatment emergent positive anti-drug antibody (ADA) results (as defined in Section 8) will be presented for both AEs and SAEs. A listing of potential immune/hypersensitivity reactions will be provided.

The following analyses (incidence proportion only) will be performed to explore the relationship between ADAs and the safety of BIIB092:

- AEs for subjects with and without treatment emergent positive ADAs
- SAEs for subjects with and without treatment emergent positive ADAs

In this study, additional samples for ADA, referred to as “event driven” samples, may be collected for subjects with hypersensitivity events. A listing of AEs for subjects with any event driven ADA samples will be provided.

6.2.4 Infusion reactions

Infusion reactions will be identified through 1) temporal association, defined as those adverse events which occur on the day of an infusion or the subsequent two calendar days after an infusion; and 2) through a custom MedDRA search of preferred terms (Appendix 11.4). A serious infusion reaction is a serious adverse event which is identified by one or both methods. An overall summary of infusion reactions will be provided with the number of subjects (n, %) with any infusion reaction; with any infusion reaction identified by temporal association only; with any infusion reaction identified through the custom search only; and any infusion reaction identified through both methods. A listing of infusion reactions will be provided. Additionally, the following incidence proportion tables will be provided:

1. Infusion reactions that occurred in temporal association to an infusion by SOC and PT
2. Serious infusion reactions that occurred in temporal association to an infusion by SOC and PT
3. Infusion reactions identified through custom search criteria by PT
4. Serious infusion reactions identified through custom search criteria by PT
5. Infusion reactions (temporal association or custom search) by 12-week intervals by PT

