Serum Anti-BIIB092 Antibody	X	See notes	X	X			Weeks 4 and 8 only. Additional event driven samples may be justified; see Section 14.
Adverse Event Reporting							
Monitor for Non-Serious Adverse Events (NSAEs)	Collection of NSAEs begins at initiation of study treatment and continues throughout the study and until 30 days following the last dose. Participants who discontinue study treatment should have an assessment of AEs 30 days after last dose. ^e						
Monitor for Serious Adverse Events (SAEs)	Following written consent to participate in the study, all SAEs whether related or not related to study treatment that occur during the screening period, continuously throughout the study, and until 30 days following the last dose, should be monitored and recorded. Participants who discontinue study treatment should have an assessment of SAEs 30 days after last dose. ^e						
Efficacy Assessments							
Progressive Supranuclear Palsy Rating Scale (PSPRS)	X		X	X	X	X	
MDS-UPDRS Part II, CGI, RBANS, PSP-QoL	X		X		X	X	
SEADL, Phonemic Fluency, Letter-Number Sequencing, Color Trails Test, MoCA	X		X	X ^f			

CONFIDENTIAL

The information contained herein may not be used, disclosed, or published without the written consent of Biogen MA Inc.

Procedure ^a	Week 0 (Day 1)	Weeks 4, 8, 16, 20, 28, 32, 40, 44 ^b (±3 days)	Weeks 12, 24, 36 (±3 days)	Week 48 (±3 days)	Week 52 (±3 days)	Early Discontinuation ^{c, d}	Notes
[REDACTED]	■		[REDACTED]	■			[REDACTED]
Magnetic Resonance Imaging (MRI)			See notes		X		Week 24 only.
Lumbar Puncture (LP)					X	X	LP should be performed prior to dosing ([REDACTED]).
Pharmacokinetic (PK) Assessments							
Blood PK Sampling	See notes	See notes	See notes	See notes	See notes		Weeks 0, 4, 24, and 48: collect predose and at EOI. Weeks 12, 36, and 52: collect predose only.
CSF PK Sampling					X	X	Collect at the time of LP ([REDACTED]).
Clinical Study Treatment Supplies							
Randomize	X						Prior to dosing for study treatment vial assignments (call should be made within 1 day prior to dosing).
Dispense Study Treatment	X	X	X	X			Duration of infusion will be at least 1 hour.

AE = adverse event; BP = blood pressure; CSF = cerebrospinal fluid; CGI-C = Clinical Global Impression of Change; CGI-S = Clinical Global Impression of Severity; [REDACTED] ECG = electrocardiogram; EOI = end of infusion; [REDACTED]

CONFIDENTIAL

The information contained herein may not be used, disclosed, or published without the written consent of Biogen MA Inc.

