6.2.5 Infusion reactions

Infusion reactions will be identified through 1) temporal association, defined as those events which occur on the day of an infusion or the subsequent two calendar days after an infusion; and 2) through a custom MedDRA search of preferred terms. The list of custom MedDRA search terms can be found in Appendix 11.2. A serious infusion reaction is a serious adverse event which is identified by one or both methods.

For the OLE period, an overall summary of infusion reactions will be provided with the number of subjects (n, %) with any infusion reaction; with any infusion reaction identified by temporal association only; with any infusion reaction identified through the custom search only; and any infusion reaction identified through both methods. Additionally, the following incidence proportion tables will be provided for the OLE period:

1. Infusion reactions (temporal association or custom search) by SOC and PT
2. Serious infusion reactions (temporal association or custom search) by SOC and PT
3. Infusion reactions (temporal association or custom search) for subjects with and without positive treatment emergent ADAs by PT
4. Serious infusion reactions (temporal association or custom search) for subjects with and without positive treatment emergent ADAs by PT
5. Infusion reactions that occurred in temporal association to an infusion by physical location of infusion (in-clinic vs. home) by SOC and PT
6. Serious infusion reactions that occurred in temporal association to an infusion by physical location of infusion (in-clinic vs. home) by SOC and PT
7. Infusion reactions identified through custom search criteria by PT
8. Infusion reactions (temporal association or custom search) by 12-week intervals by PT

Positive treatment emergent ADA will be based on the definition in Section 8 using the integrated placebo-controlled and open label extension data.

An exposure adjusted incident rate table for infusion reactions will be provided for the active treatment (placebo-controlled and OLE) period.

Additionally, the following incidence proportion tables will be provided for the active treatment (placebo-controlled and OLE) period:

1. Infusion reactions that occurred in temporal association to an infusion by physical location of infusion (in-clinic vs. home) by SOC and PT
2. Serious infusion reactions that occurred in temporal association to an infusion by physical location of infusion (in-clinic vs. home) by SOC and PT

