3 GENERAL CONSIDERATIONS

3.1 General Methods

This statistical analysis plan (SAP) only covers the analyses for the double-blind placebo-controlled portion of the study. Hereafter, the double-blind, placebo-controlled portion of the study will be referred to as “the study” in the rest of this SAP (e.g., completion of the study means completion of the placebo-controlled portion). A separate SAP will be prepared for the analyses of the open label extension (OLE) period and integrated analyses across both portions of the study. The analyses of selected exploratory endpoints may be documented separately. The term “subject” used in this SAP and in the analyses is equivalent to the term “participant” used in the Protocol.

Summary tables will be presented using descriptive summary statistics. For continuous variables, summary statistics will generally include: number of subjects with data, mean, standard deviation, median, 25% percentile, 75% percentile, minimum and maximum. For categorical variables, this

will generally include: number of subjects randomized or dosed, number with data, and the percent of those with data in each category.

In general, listings will include all data in the placebo-controlled and OLE periods (all data in the study), with an indicator of the study period (screening, placebo-controlled, or OLE) for each record to indicate when the event occurred.

Unless otherwise specified, baseline value is defined as the most recent non-missing measurement collected prior to the first dose. Change from baseline will be defined as post-baseline value minus baseline value.

Unless stated otherwise, all statistical tests will be 2-sided with statistical significance level of 0.05.

The statistical software SAS® will be used for all summaries and analyses.

The health care region used in the analysis (referred as region in this SAP) is defined as:

- US: United States
- Non-US: Australia, Austria, Canada, France, Germany, Greece, Italy, Russian, Spain, United Kingdom, Japan and Korea

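### The temporal infusion-reaction rule does not require onset after the infusion starts, so adverse events known to have begun earlier that day still count at double-blind infusions 2 to 13 and in the open-label extension

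*SAP*

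**What the plan says.** Both SAPs identify infusion reactions in two ways: by timing relative to an infusion, and by a custom MedDRA term search. This point concerns the timing rule.

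- Placebo-controlled SAP 6.2.4: temporal association is "defined as those adverse events which occur on the day of an infusion or the subsequent two calendar days after an infusion".
- OLE SAP 6.2.5: the same rule, "defined as those events which occur on the day of an infusion or the subsequent two calendar days after an infusion".

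Neither rule mentions clock time, causality or event type. The only other screen on the tables is treatment emergence. Placebo-controlled SAP 6.2.1 states "A treatment-emergent AE was defined as an AE that started or worsened after the start of first dose of study drug" and "Only TEAEs will be included in the AE tables, unless otherwise specified". The OLE SAP has the same filter, worded as the first dose of study treatment; its section 1.4 counts placebo as study treatment.

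The emergence rule does use clock times. One of its missing-data clauses applies "if the start date for a particular AE was the same as the first dose date, and the start time was missing", and another compares a stop date and time with the first dose date and time.

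Both SAPs report separately the subjects identified by timing only, by search only, and by both methods.

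**The concern.** An event that precedes an exposure cannot be a reaction to it. The window opens at midnight on the infusion day, so it includes the hours before the infusion. The treatment-emergence filter closes that gap only at the first dose.

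The consequences differ by period. In the double-blind period the same rule applies to both arms, so pre-infusion events add background to each and slightly shrink any real difference. In the OLE there is no concurrent control, so they go straight into the reported rate.

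Two OLE SAP displays could be tilted as well as noisy:

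- **In-clinic versus home infusion.** Protocol 5.1.4 rules out home visits when clinical scales, lumbar punctures or MRI are performed. Any AE arising from pre-dose procedures can therefore fall only in the in-clinic column.
- **Early versus late start, active-treatment period.** The late-start group's first BIIB092 infusion is at Week 52, where a lumbar puncture may be done the same day. The early-start group's first BIIB092 infusion was at Week 0, after a puncture no later than Day -1 and with the emergence filter in force.

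**Working it through.** The plan gives no figure for this rule, so there is none to reproduce. The check traces which infusions are exposed and then sizes the effect.

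**1. Infusions exposed in the double-blind period.** Protocol 5.1.1 gives dosing every 4 weeks with the last dose at Week 48: 48/4 + 1 = 13 infusions, matching the stated maximum of 13. At infusion 1, an AE with a known pre-dose start is not treatment-emergent and leaves the tables. At the other 12 of 13 (92%), every AE with onset after the first dose passes the filter, whatever its timing relative to that day's infusion.

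**2. Infusions exposed in the OLE.** For former placebo subjects, read literally, the filter was used up at their Week 0 placebo dose and does nothing at Week 52. OLE SAP 6.1.4 defines a separate first dose for active-treatment incidence rates, but 6.2.1 does not carry that definition into emergence. The laboratory, ECG and antibody window tables in the placebo-controlled SAP end that period on the day before the first OLE dose. If AEs follow the same boundary, the whole Week 52 dosing day belongs to the OLE.

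**3. Lumbar puncture against infusion days.**

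| Scheduled puncture | Relation to infusion |
|---|---|
| Screening, up to Day -1 | Not on an infusion day |
| Week 52, "LP should be performed prior to dosing" | First open-label infusion |
| Early Discontinuation | No dosing |
| Week 100 | Open-label infusion |

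Double-blind infusion days with a scheduled puncture: 0 of 13. OLE infusion days with one: 2, Weeks 52 and 100, if done on the same day.

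**4. Size of the window.** 13 infusions × 3 calendar days = 39 days; 39/364 = 10.7% of the double-blind period.

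**5. Share of the window before the infusion.** The infusion start hour h is not in the documents; assume 08:00 to 14:00. For a fully dosed subject, the pre-infusion hours at infusions 2 to 13 are 12h. The total window, with infusion 1 already filtered, is 13 × 72 − h.

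- h = 8: 96 / 928 = 10.3%
- h = 10: 120 / 926 = 13.0%
- h = 14: 168 / 922 = 18.2%

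**6. Effect on the reported proportion.** Assume background AEs arise at a constant rate λ per subject-year, unrelated to infusion. The chance of at least one in the window is 1 − exp(−λ × hours / (24 × 365.25)). With h = 10, the window is 926 hours under the present rule and 13 × 62 = 806 hours if onset must follow the infusion start.

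| Assumed λ | Present rule | Onset at or after start |
|---|---|---|
| 2 | 19% | 17% |
| 4 | 34% | 31% |
| 8 | 57% | 52% |

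**7. Effect on a between-arm difference.** If background events are independent of true reactions, the observed risk difference is the true one times (1 − background proportion). At λ = 4 the ratio of present to corrected rule is (1 − 0.345)/(1 − 0.308) = 0.655/0.692 = 0.947, so the present rule shrinks the difference by about 5% relative to the corrected one.

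**The case against.** A broad calendar-day net is a defensible screen. It tolerates missing times, both SAPs split the counts by method, and the custom-search tables supply a more specific definition. Infusion reactions are not among the primary safety endpoints, and the placebo arm under the same rule gives a background reference for the OLE. Most coincidental events come after the infusion and would still be counted under a corrected rule.

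Much of this stands and limits the weight of the point. It does not remove it. The timing-only count still mixes events before and after the infusion. The first two incidence tables in placebo-controlled SAP 6.2.4, and the in-clinic versus home tables in OLE SAP 6.2.5, use the timing rule alone. Tolerance of missing times can be kept without counting events known to precede the infusion.

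A reader might also infer three stronger things that the documents do not support:

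- **That post-puncture AEs contaminate the double-blind tables through a same-day procedure.** That SAP states "This statistical analysis plan (SAP) only covers the analyses for the double-blind placebo-controlled portion of the study", and no double-blind infusion day has a scheduled puncture. Even in the OLE the overlap is conditional. Punctures appear to be done in a subset whose description is redacted. Table 2 of the protocol lets the Week 52 visit spread over up to three consecutive days. The screening note holds dosing until a puncture-related AE has resolved; whether that also applies at Week 52 is not stated.
- **That all 13 infusions are affected.** The first is already filtered in the tables unless the start time is missing.
- **That pre-dose testing accompanies every infusion.** Protocol Table 2 places the efficacy scales at Weeks 0, 12, 24, 36 and 48 among double-blind dosing visits. The other 8 of 13 have none. Nothing in the documents shows that AEs actually cluster before dosing.

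**Conclusion.** The point holds, as a minor one. Both SAPs count AEs known to have begun before the infusion on the same day, at double-blind infusions 2 to 13 and at OLE infusions. In the double-blind period this is mainly shared noise. In the OLE it inflates an uncontrolled rate. It can also raise the in-clinic count relative to home and, if a Week 52 puncture falls on the dosing day, the count at the late-start group's first BIIB092 infusion.

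The size is a few percentage points: about 34% to 31% of fully dosed double-blind subjects at 4 background AEs per subject-year and a 10:00 start, and 2 to 5 points across rates of 2 to 8. The start hours, the AE rates and their constancy over the day are assumptions. Events concentrated around pre-dose procedures would add to this by an amount the documents do not let one estimate.

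**What to change.** In placebo-controlled SAP 6.2.4 and OLE SAP 6.2.5, define temporal association as onset or worsening at or after the start of that infusion, through the second following calendar day. On the infusion day, compare the AE start time with the infusion start time, and keep the AE if either is missing.

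The cost is one sentence in each SAP and a date-time comparison in programming. The emergence rule already uses AE start time and first dose date and time. Start times for later infusions are assumed to be recorded; where they are not, the event stays counted, so no plausible reaction is lost.

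A flag for AEs the investigator attributes to lumbar puncture is not requested. Appendix 3 of the protocol records causality only as related or not related to study treatment, and the documents show no field for attribution to a procedure.
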